Aim 1. Characterize the baseline time profile of the rsfMRI outcome measures in chronic SCI patients, acquired over 4 weeks of passive (sham) cycling. In order to quantitatively assess the sensitivity of rsfMRI outcome measures to early functional reorganization that occurs in response to FES cycling, baseline time profile of the outcome measures in the absence of the active stimulation must be established. Accordingly, patients will participate in a 4-week passive cycling program. At weeks 0, 2, and 4, sensory and motor network BNC (calculated using ICA- and SCA-derived brain parcels) and ISNCSCI scores will be measured. *Hypothesis: we will observe stable baseline measures of sensory and motor cortex BNC and ISNCSCI scores of the patients during the 4-week passive cycling program, with minimal to no change in values.*

Aim 2. Characterize the time profile of the cortical reorganization in chronic SCI patients that occurs during a 4-week FES cycling program. *Hypothesis: We will observe early sensorimotor cortex BNC changes after 2 weeks of FES cycling, that are predictive of changes in ISNCSCI scores at week 4.* Specifically, we hypothesize that: a) Changes in sensory network BNC at week 2 will correlate with changes in sensory ISNCSCI scores at week 4; b) Changes in motor network BNC at week 2 will correlate with changes in motor ISNCSCI scores at week 4. To test these hypotheses, we will first measure the sensory and motor network BNC and ISNCSCI scores at weeks 0, 2, and 4, then correlate the changes in sensory and motor network BNC at week 2 with the changes in respective ISNCSCI scores at week 4. Finally, longitudinal (pre- and post- intervention) inter- and intra-subject reproducibility of the ICA- and SCA-derived parcels will be assessed.

3. Background (briefly describe pre-clinical and clinical data, current experience with procedures, drug or device, and any other relevant information to justify the research)

Spinal Cord Injury and Rehabilitation.

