Secondary	FES cycling parameters	During intervention	The degree of electrical stimulation is adjusted specifically for each patients, depending on the patients level of sensory and motor impairment, as well as the patient's level of tolerance for sensation and fatigue. Accordingly, the strength and frequency of the electrical stimulation applied during each FES cycling session will be recorded. The duration of the cycling session performed will also be recorded. These parameters may be used as higher-order confounds during statistical data analysis
Secondary	Passive cycling parameters	During intervention	The amount of time and the degree of resistance used by the patients during the passive cycling sessions will be recorded, and may be used as higher-order confounds during statistical data analysis.
Secondary	Personal information	Baseline	Patient's age, sex, handedness, and time since injury will be recorded, and may be used as higher-order confounds during statistical data analysis.
Secondary	SCIM	baseline, mid-intervention, post-intervention	The Spinal Cord Independence Measure Version III (SCIM-III) assesses daily living and mobility activity performances. Specifically, it assesses the degree of self-care (feeding, grooming, bathing, and dressing), respiration and sphincter management, and mobility abilities (bed and transfers and indoors/outdoors) and each category are scored using the SCIM questionnaire. SCIM-III is frequently used in both clinical practice and clinical trial settings and is used to help guide clinicians in determining treatment goals and objectives for patients with an SCI.

c. Statistical plan including sample size justification and interim data analysis.

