Preliminary study: In this preliminary study, we hypothesized that BNC of sensorimotor and visual networks will correlate with the total ISNCSCI score, and performed the study to determine the feasibility of a larger population study. Twelve SCI patients were recruited, and the relationship between the ISNCSCI score and BNC measurements was examined. ISNCSCI sub-scores were first obtained, which were: total upper and lower body motor scores, and total sensory score. The sum of the three scores provided the total ISNCSCI scores. Analysis of the data consisted of preprocessing, PCA, and GICA, and total of 14 intrinsic functional components were identified. BNC between the sensorimotor and visual networks were computed, and plotted against the total ISNCSCI scores. Linear regression analysis was performed to find the best linear fit for the plots. Stronger BNC between the sensorimotor and visual networks was associated with lower total ISNCSCI scores ($R^2=0.35$, $p = 0.04$; [Figure 2](#)[Figure 2](#)). In other words, patients with greater degree of physical impairment tended to have stronger functional connectivity between the sensorimotor and visual networks, suggesting compensatory plastic cortical changes that are related to clinical presentation of the patients. Overall, BNC measures showed good correlations with the total ISNCSCI scores, supporting our hypothesis.

Between network connectivity (BNC) measurements from the above preliminary study provided means, standard deviations, and correlation coefficients for 12 SCI patients. A power analysis¹ revealed that a sample size of 24 subjects will be required to achieve 80% power at an alpha of 0.018; the alpha level was lowered with the correction for multiple comparisons in mind. We will therefore recruit a total of 48 patients. At this point, we do not have enough information about the variability of the BNC in response to the FES to perform a more stringent power analysis. We will use the data in the first 24 SCI subjects recruited to the study to assess the degree of variability in the metric. Based upon these estimates, we will then perform a power analysis to determine how many more subjects will need to be enrolled to assess the significance of our findings.

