The spatial maps of ICA- and SCA-derived brain parcels will be compared across groups. First, the participant-specific sensory and motor brain parcels will be converted to z values, so image intensities reflect the degree to which the parcel is present in each participant's data. The brain parcels will be combined in a second-level random effects analysis using a two sample t-test in SPM8. Voxels that contributed unequally to the parcels across groups will be identified using a liberal voxel-wise p value of 0.01 and a cluster-level p value of 0.05 corrected for multiple comparisons². The between network connectivity (BNC) between sensory and motor parcels will be calculated using Pearson's correlation coefficient between pairs of participant specific motor and sensory brain parcels³. Pairwise-correlations will be converted to Z-scores using Fisher's transformation, and the BNC across groups will be compared using two-sample t tests and adjusted p-values using a false discovery rate correction. Next, we will investigate whether sensory and motor BNC measured at week 2 of cycling program are related to motor and sensory International Standards for Neurological Classification of Spinal Cord Injury (ISNCSCI) scores measured at week 4, using a multivariate linear regression model analysis. Finally, the longitudinal inter- and intra-subject reproducibility of the ICA- and SCA-derived brain parcels will be assessed using intra-class correlation coefficient (ICC).

d. Early stopping rules.

[figure not shown]

Figure 2. Correlations between sensorimotor-visual BNC measurements and total ISNCSCI scores in SCI patients suggest a compensatory plastic cortical changes that are related to clinical presentation of the patients. Patients with lower ISNCSCI score showed larger degree of functional connectivity between the sensorimotor and visual networks.

Date: 4.14.2023

Principal Investigator: [name].

Application Number: IRB000182576

The principal investigator may discontinue the study if the interim statistical analysis as described above indicates that the number of subjects required for this trial exceeds 50.

Patients may withdraw from the study at any time for any reason. Any investigator may discontinue a patient for any of the following reasons:

- The subject experiences a medical emergency that necessitates discontinuation of therapy

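### Section 7c relates week-2 BNC level to week-4 ISNCSCI level, whereas Aim 2 calls for change against change; as written it does not test Aim 2 and could report a stable severity link as early prediction

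*Combined protocol and SAP*

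**What the plan says.** Section 2, Aim 2 sets out two hypotheses, both change against change. For the sensory side: "Changes in sensory network BNC at week 2 will correlate with changes in sensory ISNCSCI scores at week 4". For the motor side: "Changes in motor network BNC at week 2 will correlate with changes in motor ISNCSCI scores at week 4". It then gives the analysis: measure BNC and ISNCSCI at weeks 0, 2 and 4, and "then correlate the changes in sensory and motor network BNC at week 2 with the changes in respective ISNCSCI scores at week 4".

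Section 7c gives a different analysis. It will examine "whether sensory and motor BNC measured at week 2 of cycling program are related to motor and sensory International Standards" "scores measured at week 4, using a multivariate linear regression model analysis". Predictor and outcome are both levels at a single visit. No change score, baseline BNC or baseline ISNCSCI is named, and neither the arm nor the alpha for this regression is given.

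Section 7b lists optional covariates: "age, sex, handedness, and time since injury will be recorded, and may be used as higher-order confounds during statistical data analysis", with cycling parameters described in the same way. Neither baseline is among them.

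The preliminary study in 7c reports a cross-sectional link: "Stronger BNC between the sensorimotor and visual networks was associated with lower total ISNCSCI scores", with R² = 0.35 and p = 0.04 in 12 patients. No intervention is mentioned in that report.

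**The concern.** The two sections specify different analyses, and nothing in the document reconciles them. They also answer different questions. Section 5 admits ASIA grades A to D, so patients differ widely in severity before any cycling. If more impaired patients have different connectivity throughout, week-2 BNC will be associated with week-4 ISNCSCI even when nobody's BNC change says anything about their recovery. Section 4e expects minimal neurological difference between the arms over 4 weeks. If scores do move little, week-4 scores will largely repeat week-0 scores.

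Aim 2 carries the trial's main claim, that resting-state fMRI is an early biomarker of recovery. A significant 7c result could be taken as support for that claim without being evidence for it. The reverse error is also possible: a real link between changes can be swamped by stable differences between patients and missed. Leaving both versions in place also allows the choice between them to be made after the data are seen.

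**Working it through.** **1. The plan's own figures.** The pilot gives |r| = √0.35 = 0.592 with n = 12.
- Test: t = 0.592 × √(10/0.65) = 2.32 on 10 df, p = 0.043, which agrees with the stated 0.04.
- Fisher-z 95% interval: atanh(0.592) = 0.680; 0.680 ± 1.96/√9; back-transformed, 0.03 to 0.87.
- Sample size: 7c states 24 subjects for 80% power at alpha 0.018, without effect size or sidedness. Assuming a test of one correlation at the pilot r, n = ((2.366 + 0.842)/0.680)² + 3 = 25.2, so 26 two-sided; the one-sided version gives 22. Simulated two-sided power at n = 24 is 0.787. The stated 24 is therefore consistent with a sample size built on a level-on-level correlation, though this is an inference.

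**2. False prediction.** BNC (weeks 0 and 2) and ISNCSCI (weeks 0 and 4) were simulated as stable, correlated patient traits plus independent visit error, with changes unrelated (40,000 replicates). Assumed reliabilities for (BNC, ISNCSCI) were (0.5, 0.95), (0.7, 0.95) and (0.9, 0.98); level-on-level results differed by less than 0.01 between them. Because 7c gives no alpha for this regression, 0.018 is borrowed from the sample-size paragraph and 0.05 is shown beside it.

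| Persistent cross-sectional r (assumed) | 7c model, n = 24, alpha 0.018 | 7c model, n = 48, alpha 0.018 | 7c model, n = 24, alpha 0.05 |
|---|---|---|---|
| 0.03 | 2% | 2% | 5% |
| 0.2 | 8% | 16% | 16% |
| 0.3 | 17% | 39% | 30% |
| 0.4 | 34% | 69% | 51% |
| 0.59 | 79% | 99% | 89% |

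Other models under the same conditions, at alpha 0.018:
- Change on change: 1.7% to 1.9% throughout.
- Week-4 ISNCSCI on week-2 BNC with both baselines as covariates: 1.8% to 2.8% (n = 24) and 1.8% to 4.0% (n = 48). The upper ends occur at r = 0.59 with BNC reliability 0.5.
- Adjusting for baseline ISNCSCI only: up to 3.4% (n = 24) and 5.6% (n = 48), so both baselines are needed.

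**3. Missed signal.** Suppose the true change-change correlation is 0.6, baselines are independent of each other and of the changes, n = 24 and alpha is 0.018. Let b and y be SD(change)/SD(baseline) for BNC and ISNCSCI. The correlation that the level-on-level model sees is 0.6·b·y / √((1 + b²)(1 + y²)).

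| b, y (assumed) | Correlation of levels | 7c model detects | Change on change detects |
|---|---|---|---|
| 0.5, 0.2 | 0.05 | 2% | 81% |
| 0.7, 0.3 | 0.10 | 3% | 81% |
| 1.0, 0.5 | 0.19 | 7% | 81% |

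**4. Power of the Aim 2 analysis.** The documents give no correlation or variance for the changes, so the required n cannot be computed. The correlation detectable with 80% power at two-sided alpha 0.018 is tanh((2.366 + 0.842)/√(n − 3)): 0.60 at n = 24 and 0.44 at n = 48.

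**5. Pooling arms.** If all 48 patients are pooled without an arm term, and treatment shifts both changes by 0.5 or 1 SD (assumed), an unrelated pair of changes is declared related in 2.8% or 15.6% of trials at alpha 0.018. With an arm term the rate is 1.8%.

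**The case against.** The strongest reply is that Aim 2 already prespecifies the right analysis, in two hypotheses and an analysis sentence, and that the 7c sentence is a one-line summary whose reference to multivariate regression does not exclude baseline terms. It is true that the Aim 2 test is not absent from the document. But 7c is the statistical plan, it describes a different predictor and outcome, and no baseline term is named anywhere.

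Several narrower points stand in part:
- **Covariate list.** The covariates in 7b are not called exhaustive, and primary outcomes would not be expected in that table. Their absence is only weak evidence.
- **Arm.** Aim 2 is framed around the FES programme, so the intended arm can be inferred. The 7c wording remains loose.
- **Size.** The 79% and 99% figures need r = 0.59, which comes from sensorimotor-visual BNC and total ISNCSCI in 12 patients. The trial uses other BNC pairs and separate scores, and is limited to T1 to L2 injuries. At r = 0.1 the rates are only 2.9% (n = 24) and 4.6% (n = 48). The percentages are illustrative; the direction is not in doubt.
- **Change on change is not immune.** Both changes share week 0, and section 4 schedules the clinical evaluations to coincide with the MRI dates. If week-0 errors correlate at 0.3 (assumed, with equal error variance at each visit), change on change rejects in about 4.8% (n = 24) or 8.8% (n = 48) of trials with no true link. This is still far below the level-on-level rates at moderate r.
- **Definition of BNC.** 7c defines BNC between sensory and motor parcels, while Aim 2 needs a sensory-network and a motor-network measure, each matched to its own score. This also needs aligning.
- **Power.** The document does not tie its 80% power to this analysis, and it concedes that "we do not have enough information about the variability of the BNC in response to the FES to perform a more stringent power analysis". The caution about power is therefore preventive.

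**Conclusion.** The concern holds. Section 7c contradicts Aim 2, and followed as written it does not test the hypothesis on which the biomarker claim depends. That conclusion comes from the text alone and needs no numerical assumption.

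The size of the harm does depend on assumptions: how large a cross-sectional link exists for the BNC measures used here, and whether it persists over 4 weeks. At moderate r (0.3 to 0.4), false prediction runs at 17% to 34% with n = 24 and 39% to 69% with n = 48, against a nominal 1.8%. Near r = 0 there is no inflation, but the 7c model can then still miss most of a strong true link between changes. This should be fixed before analysis. It does not call the trial's design or data collection into question.

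**What to change.** Rewrite the 7c sentence to match Aim 2, and name one of these models as the planned analysis:

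1. Regress ISNCSCI change (week 4 minus week 0; sensory and motor separately) on the respective BNC change (week 2 minus week 0, on the Fisher-z scale). This is the literal Aim 2 analysis.
2. Regress week-4 ISNCSCI on week-2 BNC with baseline ISNCSCI and baseline BNC both as covariates. This estimates a conditional association, and its error rate can reach about twice nominal when BNC is noisy.

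In the same edit:
- Run the analysis in the FES arm, or include a treatment-arm term if arms are pooled.
- State the alpha.
- Define the sensory-network and motor-network BNC that serve as predictors.
- Report the level-on-level association as descriptive only.
- Do not claim the stated 80% power at n = 24 for this analysis.

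The cost is wording. Week 0, 2 and 4 values are already collected, so no visit or scan is added. The main downside is that power for change on change is unknown: 80% power needs a correlation of about 0.60 with 24 patients or 0.44 with 48. The possible effect of shared week-0 error should be noted as a limitation.

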development of a robust, clinically feasible rsfMRI data analysis pipeline, this study is expected to result in improved understanding of the functional reorganization that takes place during and after intervention.

4. Study Procedures

- Study design, including the sequence and timing of study procedures (distinguish research procedures from those that are part of routine care).

This will be an early phase 1 (phase 0) clinical trial. Specifically, the study will be performed as a randomized, parallel group trial to determine if the amount of changes in brain functional connectivity outcome measures (i.e., between network connectivity) is significantly different between the group of patients that perform FES cycling and another group of patients that perform passive (sham) cycling.

Patients of the International Center for Spinal Cord Injury (ICSCI) at the Kennedy Krieger Institute (KKI) will be identified as meeting the inclusion criteria by reviewing the medical records held by the ICSCI. Once the patient consents by signing the consent form, official screening of subjects will be performed. Subjects will be randomized into 2 groups: FES cycling (Group 1; n=24) and passive cycling (Group 2; n=24). The patients will undergo either an FES cycling or a passive cycling sessions for 4 weeks, 3 times a week. **Acquisition of rsfMRI measures:** MRI will be performed on all participants at the beginning (prior to cycling sessions) and at the end of the 2nd and 4th weeks of the intervention program. **Acquisition of clinical measures:** ISNCSCI and SCIM (Spinal Cord Independence Measure) evaluations will be performed to coincide with the dates of MRI acquisitions, to determine the neurological level and the degree of sensory and motor impairments. Detailed study timeline can be found in Figure 1.

[figure not shown]

Figure 1. Study Timeline.

- SCI patients assigned to FES cycling group will take part in the following evaluations:
 - Medical chart review / MRI screening questionnaire
 - FES cycling trial
 - Neurological evaluation (ISNCSCI – more commonly known as ASIA exam)
 - Functional evaluation (SCIM)
 - MRI

Date: 4.14.2023

Principal Investigator: [name].

Application Number: IRB000182576

E1: FES cycling

- SCI patients assigned to passive cycling group will take part in the following evaluations:
 - A: Medical chart review / MRI screening questionnaire
 - B2: Passive cycling trial

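### Section 7c does not carry over Aim 2's specification: the week-2 BNC / week-4 ISNCSCI regression names no arm and uses levels, whereas Aim 2 concerns changes under FES cycling

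*Combined protocol and SAP*

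**What the plan says.** Section 2 gives each arm its own aim. Aim 1 covers the control: "patients will participate in a 4-week passive cycling program". Aim 2 is to "Characterize the time profile of the cortical reorganization in chronic SCI patients that occurs during a 4-week FES cycling program". Its hypothesis is that BNC change after two weeks of FES predicts ISNCSCI change at week 4, sensory network with sensory score and motor network with motor score. The analysis described there is change against change.

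The only matching analysis in Section 7c asks "whether sensory and motor BNC measured at week 2 of cycling program are related to motor and sensory International Standards", meaning the ISNCSCI scores measured at week 4, using a multivariate linear regression. No arm is named, and arm is not listed as a model term. Section 2 speaks of a cycling program for passive and for FES cycling alike, so the phrase does not settle the population. Section 7b lists optional confounders (cycling parameters, age, sex, handedness, time since injury); arm is not among them. The same paragraph of 7c does use arm for the parcel maps and for the two-sample t tests on BNC.

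On size, 7c states that "a sample size of 24 subjects will be required to achieve 80% power at an alpha of 0.018", and then "We will therefore recruit a total of 48 patients". Section 4a allocates 24 to each group.

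**The concern.** This regression is the only planned test of the trial's predictive claim, that early BNC change foretells neurological improvement in response to an intervention. Two features of Aim 2 are lost between the objective and the analysis.

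- **Population.** With no arm named, the fit may use 24 or 48 patients, and the choice could be made after the results are seen.
- **Variable.** Levels at weeks 2 and 4 carry the stable differences between patients. The pilot in 7c already reports a level-on-level relation in SCI patients, with no FES program described. A positive result on levels could restate that finding.

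If both slips stand, a significant coefficient could not be read as evidence that BNC tracks response to FES.

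**Working it through.** **Inputs.** Alpha 0.018, 80% power, n = 24 and pilot R-squared 0.35 with n = 12 (Section 7c); 24 per arm (Section 4a). Assumptions: the pilot R-squared was the input to the power analysis, and its size carries over to Aim 2. The pilot used sensorimotor-visual BNC and total ISNCSCI, a different quantity. The documents do not state sidedness; two-sided tests are used unless noted. Simulated rates are for 24 + 24 bivariate normal patients, 20,000 trials or more.

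**1. The plan's own figures.** r = sqrt(0.35) = 0.592. Pilot p: t = 0.592 × sqrt(10/0.65) = 2.32 on 10 df, p = 0.043, against the stated 0.04. Sample size for a correlation: n = ((z_alpha + z_power)/atanh(r))² + 3.
- Two-sided: ((2.366 + 0.842)/0.680)² + 3 = 25.2, so 26.
- One-sided: ((2.097 + 0.842)/0.680)² + 3 = 21.7, so 22.
- One-predictor F test: 23.

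The stated 24 is thus consistent with a correlation test in one group of 24. Simulated two-sided power at n = 24 is 78% to 79% (Fisher-z 77%).

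**2. A general relation, not specific to FES.** Let r = 0.592 in both arms. Pooled, n = 48: 0.680 × sqrt(45) − 2.366 = 2.20, so power is 98.6%; simulation agrees. An FES-only fit on levels is positive about 79% of the time. The arm-by-BNC interaction rejects about 1.9% of the time, which is its nominal rate. Only the interaction distinguishes this case.

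**3. A relation under FES only.** Let r = 0.592 in FES and 0 in passive, with no mean shift and a passive SD of q times the FES SD in both variables. Then pooled r = 0.592/(1 + q²).

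| q | Pooled r | Pooled power, alpha 0.018 |
|---|---|---|
| 1 | 0.296 | 38% |
| 0.75 | 0.379 | 62% |
| 0.5 | 0.473 | 83% to 84% |
| 0.2 | 0.569 | 93% |

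The FES arm alone has about 78%. At alpha 0.05 with q = 1 the figures are 89% (FES alone) and 54% (pooled). Equal SD suits levels, because randomised chronic patients should vary similarly in both arms. A smaller q suits change scores if passive patients stay stable, as Aim 1 expects.

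**4. A relation created by arm shifts.** With no correlation inside either arm and shifts of dx (BNC) and dy (ISNCSCI) in SD units, pooled r = (dx·dy/4)/sqrt((1 + dx²/4)(1 + dy²/4)).
- dx = 0.8, dy = 0.2: r = 0.04/1.082 = 0.037. Positive about 5.5% to 6% of the time at nominal 5%, and 2.2% at 0.018.
- dx = dy = 0.8: r = 0.16/1.16 = 0.138. Positive about 16% at 5%, and 7.3% at 0.018.

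**5. The interaction, r = 0.592 against 0, equal SD.** Fisher-z: 0.680/sqrt(2/21) − 2.366 = −0.16, so 44% at alpha 0.018. Simulation gives about 38% at 0.018 and about 54% at 0.05. For 80% at 0.018: 2 × (3.208/0.680)² + 3 = 47.5, so about 48 per arm (96 in total).

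**The case against.** The strongest reply is that the restriction is already in the document. Aim 2 names the population and the variables, and Section 7c serves the aims. Read together, the test is change on change in the FES arm, with about 78% power under the pilot correlation. This stands. A reader might infer that no reading of the plan tests the Aim 2 hypothesis, and the documents do not support that. The defect is that 7c, which will govern the analysis, says something else.

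A reader might also infer that an FES-only fit throws away the randomised control. It does not: Section 4a makes the between-arm difference in BNC change the design question, 7c compares BNC across groups, and Aim 1 profiles the passive arm. The control goes unused only for the slope.

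Two harms are easily overstated. Pooling does not always halve power; step 3 shows that this depends on the passive arm's spread. Nor is a relation manufactured by arm shifts a main risk. Section 4e expects minimal neurological differences between the arms, and step 4 shows near-nominal error in that case.

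Finally, specificity to FES is not a stated Aim 2 hypothesis, and the study calls itself early phase 1. That is a reason to treat the interaction as supportive. It is not a reason to leave the analysis set and the variable undefined.

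**Conclusion.** The concern holds as an inconsistency between the objective and the analysis plan. Section 7c omits both the FES restriction and the change scores that Aim 2 specifies.

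The main consequence is interpretive. If a pilot-sized level relation exists in both arms, the regression as written on all 48 patients is positive about 99% of the time at alpha 0.018 whether or not anyone responds to FES. Loss of power is a second, conditional consequence: 78% to 38% with equal spread, 62% pooled at an SD ratio of 0.75, and no loss at about 0.5. A relation created by arm shifts is minor unless ISNCSCI also shifts substantially.

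An FES-only change-score fit tests Aim 2 literally, but cannot alone show that the relation is specific to FES rather than prognostic or common to any cycling. All sizes rest on r = 0.59 being transferable from a 12-patient pilot of a different BNC pair. The arm shifts and SD ratios are assumptions shown as ranges.

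**What to change.** In Section 7c, replace the sentence with one model on all randomised patients. Regress ISNCSCI change to week 4 on BNC change to week 2 (or use the week values adjusted for their baselines), with arm and arm-by-BNC terms. Fit it for the two pairs in Aim 2: sensory BNC with sensory score, and motor BNC with motor score.

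- Name the FES-arm slope as the Aim 2 test.
- Report the passive-arm slope, and the interaction with its confidence interval, as supportive and not as a significance gate.
- Describe BNC as specific to FES response only as far as that interval supports; otherwise call it a correlate of change under cycling.
- Let the residual variance differ by arm. If passive patients are more stable, a common variance would make the standard error of the FES slope too small.

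The cost is SAP wording and two model terms, with no new data or patients. The downside is imprecision: the interaction has only about 38% power at alpha 0.018 (about 54% at 0.05) under r = 0.59 against 0, and the plan should say so.
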